#### Volunteer recruitment

Volunteers will be staff and students recruited from Queen's University Belfast. Involvement in the study will be advertised via poster advertisement around university buildings initially in the David Keir Building (DKB), Sonic Arts Research Centre (SARC) and Northern Ireland Technology Centre (NITC). Following this, advertisement posters will be displayed in the

Date: 22/03/2019

Medical Biology Centre (MBC). Volunteers will also be recruited via university mailing lists and through inclusion of the study advertisement on the staff round-up. All potential volunteers will be given the information sheet and will be assessed for suitability and eligibility using a short screening questionnaire which will identify whether volunteers fit into the inclusion and exclusion criteria (see below). Subsequently, participants will be given 48 hours to decide whether or not to participate in the study. When participation is agreed written consent will be obtained.

### Inclusion and exclusion criteria

Potential participants will be screened using an eligibility questionnaire (See attached questionnaire), which will identify suitable participants by applying specific inclusion and exclusion criteria outlined below. Male and female healthy volunteers aged between 18-64 years old will be considered for participation. For eligibility of participation, volunteers must be non-smokers, must not be taking statins to lower LDL cholesterol levels and must not have high blood pressure (systolic >140/ diastolic >90mmHg). Moreover, participants with a BMI of <18.5 kg/m² and greater than >35 kg/m² will be excluded. Participants who are taking prescribed medication and any form of dietary supplements will also not be eligible to participate The consumption of the lamb meat will act as a substitute for optimal habitual red meat consumption as recommended by the WCRF and UK NHS. Therefore, participants must be red meat consumers and willing to consume three portions of lamb per week. Participants who consume more than two portions of fish per month will also not be eligible to participate, as that may mask the ability of the lamb to affect n-3 PUFA status.

#### Blood collection and handling

Blood samples (25ml) will be taken at the beginning of week 0 and end of week 4 (end of dietary intervention) from both the grass-finished meat and concentrate-finished meat treatment groups. As total-cholesterol, HDL-cholesterol and triglyceride concentrations will be measured participants will be asked to fast for 12 hours prior to blood being taken. Samples will be taken, separated within 1 hour of collection and then stored at -80°C until analysed at a later date. Plasma and serum will be harvested by spinning blood samples at 2500 g for 15 minutes, whilst platelets will be harvested by centrifuging blood samples at 150 g for 15 minutes. Samples will be analysed for the fatty acid composition of blood plasma and platelet, in addition to total cholesterol, HDL-cholesterol and triglycerides (by commercially available kit on a Randox Daytona autoanalyser). All blood will be taken by a trained phlebotomist and stored and analysed at the Centre for Public Health, Queen's University Belfast.

Date: 22/03/2019

Blood plasma, platelet and serum aliquots will be analysed for fatty acids using gas chromatography at the Centre for Public Health, Queen's University Belfast. Lipids will be extracted using the Folch method (Folch et al. 1957) and methyl esters will be prepared using an adaption of the method outline by Morrison et al. (Morrison et al. 1964). Fatty acid composition will be analysed using gas chromatography (Hewlett Packard 6890 Gas Chromatograph) and flame ionizing detector. Peaks will be integrated using 'Chemstation' computing integrator. Fatty acid methyl esters will be identified by output retention times which will be compared to known and commercially available standards. Results will be presented initially as % of total fatty acid content and then will be quantified by looking at retention times, peak areas and the use of an internal standard.

#### Blood Pressure and BMI

Blood pressure and body mass index (BMI) will also be assessed at baseline (week 0) and post-intervention (week 4) from both the grass finished meat and concentrate finished meat treatment groups. Blood pressure will be taken using an automated sphygmomanometer using established Centre for Public Health SOPs. Blood pressure from all participants will be taken from the same arm to ensure consistency. Systolic and diastolic pressure will be measured and recorded. BMI will be calculated by assessing the participant's weight (kilograms) and height (metres squared). Assessment will take place at The Centre for Public Health, Queen's University Belfast. Blood pressure and BMI data will be taken by [name] (PhD researcher).

#### Illness during the study

During the study, if a participant feels unwell as a result of eating the lamb, participants should contact the researchers using the phone number or email address provided on the participant information sheet. There is minimal risk of discomfort as a result of consuming the lamb, however if discomfort does occur, participants can opt out of the study at any given stage. Participants should seek medical advice if it is felt this is appropriate.

#### Incidental findings

It will be made clear to participants that during data analysis the researchers are not looking for anything other than what is stated in the information sheet. Nonetheless, if any incidental findings are discovered (e.g. hypertension), the research team is obliged to disclose this

Date: 22/03/2019

information with the participants. If an incidental finding occurs, the researchers will advise participants to consult a GP or a medical professional who will be able to guide them further.

#### Planned statistical analysis of results

The change in each outcome variable will be compared between intervention groups using an independent samples t-test. A significance level of 0.05 will be used to determine statistical differences. Any effect within treatments from baseline to end of intervention will be analysed using a paired t-test. A significance level of 0.05 will be used to determined statistical differences. All statistical analysis will be carried out with the assistance of [name] and using established statistical software such as SPSS.

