## Aims and objectives

**Overall aim:** To investigate the impact of consuming grass finished lamb meat on human health parameters when compared to concentrate finished lamb meat.

**Primary objective:** To assess the effect of regular consumption of grass finished and concentrate finished lamb meat on the plasma and platelet omega-3 status of healthy individuals.

**Secondary objective:** To assess the effect of consumption of grass finished and concentrate finished lamb meat on cardiovascular risk factors including blood pressure, body mass index (BMI), total cholesterol, HDL-cholesterol and triglycerides among healthy individuals.

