### Sample size and justification

Healthy volunteers (N=38) will be recruited and allocated to one of two treatments (n=19/treatment) balanced for age and gender using a computer-generated randomization tool, which will be completed with the assistance of [name] (statistician). Sample size was determined using power calculations based on changed in blood plasma and platelet PUFA levels from a similar study (McAfee et al, 2011). Based upon the SD of plasma PUFA of 2 units (%), with 16 in each treatment there will be over 80% power to detect, as statistically significant at the 5% levels, a difference in mean PUFA of 2 units in the grass-fed lamb meat group and the concentrate fed lamb meat group. This will be determined using an independent samples t-test. This difference in plasma PUFA is similar (slightly less than) the difference seen in the previous study (McAfee et al. 2011), however it is anticipated a larger difference will be detected as only lamb meat is being used which is documented to be of increased capacity to store omega-3 PUFA (Bessa et al, 2015) and therefore it is expected that this will have a greater influence on blood plasma PUFA status. The power calculation for platelets will be more limited, however, based on the SD of platelet PUFA of 4 units (%), with 16 in each treatment we would have over an 80% power to detect, as statistically significant at the 5% level, a difference of 2 units in the lamb-fed meat group and concentrate fed meat group. In addition to the 32 required participants established by statistical power calculations an additional six participants will be recruited to account for drop out and non-compliance.

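### Comparing arms by an unadjusted t-test on change is valid but usually less precise than ANCOVA on the week-0 value already collected; the gain depends on a correlation the plan does not give

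*Combined protocol and SAP*

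**What the plan says.** The section on planned statistical analysis gives one rule for comparing the arms: "The change in each outcome variable will be compared between intervention groups using an independent samples t-test". Paired t-tests within each arm are added, and 0.05 is the significance level throughout. No section mentions ANCOVA or any covariate.

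The sample size section uses the same type of test. For plasma it states "Based upon the SD of plasma PUFA of 2 units (%), with 16 in each treatment there will be over 80% power" to detect a difference of 2 units, and adds "This will be determined using an independent samples t-test". Recruitment is 19 per arm, which allows for six losses. Allocation is "balanced for age and gender using a computer-generated randomization tool"; baseline fatty acid levels play no part in it.

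Baselines are available for everything tested. Under blood collection, "Blood samples (25ml) will be taken at the beginning of week 0 and end of week 4", in both arms. The section on blood pressure and BMI schedules those measurements at the same two time points.

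**The concern.** Subtracting the baseline assumes that a participant who starts one unit higher would finish exactly one unit higher. With equal SDs at the two visits the regression slope of week 4 on week 0 is r, which is below 1, so the change score over-corrects for any chance difference between arms at baseline. Such differences are not negligible here: at 16 per arm the standard error of the baseline difference is √(2/16) = 0.35 SD. Allocation is unlikely to remove them for fatty acids, because participants start as they are recruited and samples are stored for later analysis.

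Precision is at stake in a small trial. The stated plasma power has no margin (see the working), and a more efficient analysis would cost no participants and no new measurements.

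**Working it through.** **Inputs from the plan.** Plasma PUFA: SD 2, difference 2, 16 per arm evaluable, 19 recruited, 5% level. Two-sided testing is assumed, as the plan does not say.

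**Assumed.** The correlation r, shown from 0.3 to 0.9, and at first equal SDs at week 0 and week 4.

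**The plan's own figure.** The standardised difference is 2 / (2 × √(2/16)) = 2.83. The normal approximation gives Φ(2.83 − 1.96) = 80.7%, which reproduces the claim of over 80%. The exact noncentral t gives 78.1% at 16 per arm; 17 per arm give 80.7% and 19 give 85.1%.

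**Variance comparison.** Let σ be the common SD and N the total analysed.

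- The change-score variance is proportional to 2σ²(1 − r).
- The ANCOVA variance is proportional to σ²(1 − r²) × [1 + 1/(N − 4)], where the bracket is the average cost of estimating the slope.
- The ratio of ANCOVA to change is (1 + r)/2 × [1 + 1/(N − 4)].

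At N = 32 the bracket is 29/28 = 1.036. At r = 0.5 the ratio is 0.75 × 1.036 = 0.78. Break-even is r = 2 × 28/29 − 1 = 0.931. At N = 38 it is 2 × 34/35 − 1 = 0.943. Simulated ratios at N = 32 agree: 0.779 at r = 0.5, 0.932 at 0.8 and 0.983 at 0.9.

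**Power for plasma PUFA at 16 per arm.** The plan does not settle which SD it means, so both readings are shown: (a) SD 2 is the SD of change, where the t-test has 78.1% at every r; (b) SD 2 is the SD at a single visit.

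| r | Variance ratio | (a) ANCOVA | (b) t-test | (b) ANCOVA |
|---|---|---|---|---|
| 0.3 | 0.67 | 91% | 64% | 80% |
| 0.5 | 0.78 | 87% | 78% | 87% |
| 0.7 | 0.88 | 83% | 94% | 96% |
| 0.8 | 0.93 | 81% | 99% | 99% |
| 0.9 | 0.98 | 79% | 100% | 100% |

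Under (a) the mean 95% CI width is 2.86 units by t-test and 2.35, 2.53, 2.69, 2.77 and 2.84 by ANCOVA. At 19 per arm, power is 85.1% against about 96, 93, 89, 88 and 86%. At r = 0.95 and 16 per arm, ANCOVA has about 77.7%, a loss of about 0.4 point.

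**Unequal SDs.** Let k be the week-4 SD divided by the week-0 SD. In units of the week-0 variance, the comparison is k²(1 − r²) × 29/28 for ANCOVA against 1 + k² − 2rk for change.

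- k = 1.1: the change score is slightly better for r between about 0.79 and 0.96.
- k = 1.25: it is slightly better for r between about 0.66 and 0.89.
- k = 0.9 or 0.8: ANCOVA is better at every r.

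**Largest possible loss.** Since 1 + k² − 2rk = k²(1 − r²) + (1 − rk)², the change-score variance is never below k²(1 − r²). The ratio therefore cannot exceed 29/28, a loss of 1/28 = 3.6%, whatever r and k are.

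**The case against.** The strongest reply is that the planned test is sound, matches the test used for sizing, and suits a study described as proof of principle. That is right. A reader might infer that the t-test on change is biased or invalid; under randomisation it is neither.

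The second reply is that the benefit cannot be sized from the documents. That also stands. No correlation is given, the gain is small at r = 0.8 and negligible near 0.9, and under reading (b) the t-test already has 94% power at r = 0.7. The sample size text refers to changes in PUFA levels in the earlier study, which leans towards reading (a) without settling it. For omega-3, the stated primary objective ("plasma and platelet omega-3 status of healthy individuals"), no SD is given, so only the variance ratio applies and power cannot be computed.

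Third, a reader might take 0.93 as a general threshold. It depends on equal SDs at the two visits, which nothing in the plan supports or excludes. A reader might also infer that every comparison would tighten. An outcome with very high r, possibly BMI over four weeks, would gain nothing or lose slightly.

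None of this reverses the recommendation, because the trade is lopsided: at most 3.6% of variance lost, against about 22% gained at r = 0.5 with equal SDs. Not knowing r favours ANCOVA.

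**Conclusion.** The point holds as an inexpensive improvement in efficiency, not as a fault in the plan. With equal SDs and r = 0.5, ANCOVA at 16 per arm is worth about 16/0.78, or between 20 and 21, per arm under the planned test. Under reading (a) it brings plasma power above 80% for r up to about 0.8. Most outcomes may gain.

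These sizes rest on an assumed r, equal SDs for the tabulated figures, normal data and two-sided testing. The 3.6% cap on the loss does not depend on r or on the SD ratio.

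A reader might also infer that ANCOVA would repair the platelet calculation, which states "based on the SD of platelet PUFA of 4 units (%), with 16 in each treatment" as its basis. It would not; the platelet shortfall is a separate matter and lends this point no weight.

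**What to change.** In the planned statistical analysis section, replace the between-arm sentence with: *The week-4 value of each outcome will be compared between groups by ANCOVA, with treatment as factor and the baseline value of that outcome as covariate; the adjusted mean difference and its 95% confidence interval will be reported. A t-test on change from baseline will be a sensitivity analysis.* Settle this before week-4 results are examined, so that the choice between the two analyses cannot depend on them.

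If the team prefers to present change, ANCOVA of change with baseline as covariate gives the same treatment estimate.

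The cost is one sentence, one residual degree of freedom (30 to 29 at 16 per arm) and a possible variance loss under 4%. No new data are needed, and SPSS, which the plan names, fits the model.

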## Plan of investigation

### Study design

The study period will consist of a four-week, single blinded, randomised dietary intervention whereby participants will be required to eat three portions per week of lamb meat from one of two treatments for a four-week study period. The study will focus entirely on the consumption of lamb meat. This is because evidence in current literature suggests that lamb muscle has a higher capacity to store omega-3 in the muscle phospholipids when compared to other meats such as beef or pork (Bessa et al, 2015). Therefore, as a proof of principle study, volunteers will consume three portions of lamb per week for four weeks, substituting lamb for regular red meat consumption and therefore maintaining intakes of red meat within safe levels and not encouraging any adverse dietary pattern.

Date: 22/03/2019

Lamb portions will include per week one portion of mince (raw weight 250g) and two portions of lamb chops (raw muscle weight 235g). Raw lamb portions will total 720g per week. Literature suggests cooking losses will represent approximately 32% (Matthew and Garrison, 1975), meaning around 490g of lamb per week will be consumed, keeping below recommendations by the World Cancer Research Fund (WCRF) to consume less than 500g of red meat/week and UK NHS recommendations to consume no more than 70g/day of red and processed meat. One group of participants will receive lamb meat from concentrate finished lambs and another group will receive lamb meat from grass finished lambs. The study will be single blinded meaning researchers will know what treatment participants are receiving however participants will not be told what dietary treatment they are receiving.

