Meat will be stored at AFBI Newforge, AFBI Stormont and North South Retail Belfast. The meat will be delivered to the participant's residence frozen on a weekly basis. Days and times of delivery will be discussed and decided on an individual participant basis. Participants will also be expected to keep a three-day food diary which will be completed prior to the intervention start and then again during the mid-point of the intervention during week one and week three. This is where all food and drinks for the three days will be recorded with as much detail as possible regarding consumption (including left overs), time of day, quantity of food and cooking methods. In addition, participants will also be asked to keep a meat diary for the entire duration of the study as a record of whether all meat is consumed or whether some is not consumed. This will also include what cooking methods are used and whether participants consume the subcutaneous fat or not. Participants will receive recipe cards at the beginning of the four-week study period to provide cooking ideas; however, there is no obligation to follow the recipes. Participants may cook the lamb however they choose but will be reminded of the importance of following good food safety and hygiene practices e.g. defrosting meat safely and the importance of thoroughly cooking minced meat.

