### Project timetable

Recruitment of volunteers is planned to commence in April 2019 using poster advertisement (See Table 1). Once participants have been recruited, they will commence the dietary interventions. Participants will be stagger started as and when they are recruited. Completion of volunteer study periods are planned to finish in July 2019, at which point laboratory, data and statistical analysis will occur. The study is due to be fully completed by November 2019.

Date: 22/03/2019

**Table 1:** Proposed project timetable for recruitment, intervention study period, analysis and writing up

	Mar	Apr	May	Jun	Jul	Aug	Sep	Oct	Nov	Dec
Ethics										
committee										
Recruitment										
Commence										
study periods										
Complete study										
periods										
Laboratory, data										
and statistical										
analysis										
Writing up and										
publishing										
Study										
completion										

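### Do the within-group paired t-tests at 0.05 undermine the conclusion about grass-finished lamb?

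*Combined protocol and SAP*

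**What the plan says.** Under Planned statistical analysis of results, the first test is an independent-samples t-test on the change in each outcome between the two groups, at 0.05. The next sentence adds the paired tests: "Any effect within treatments from baseline to end of intervention will be analysed using a paired t-test". The same 0.05 level is then repeated for them. Neither test is named as the basis for conclusions, and the paired tests are not called descriptive.

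Other sections bear on how to read this:

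- Aims and objectives: the overall aim studies grass-finished lamb "when compared to concentrate finished lamb meat". The primary objective just below it speaks of the effect of both meats, which can be read as a between-group or a within-group question.
- Background, closing paragraph: the study is described as a proof of principle for a biological effect of habitual lamb eating, which is wider than grass versus concentrate.
- Study design: "One group of participants will receive lamb meat from concentrate finished lambs and another group will receive lamb meat from grass finished lambs". Both groups eat it while "substituting lamb for regular red meat consumption".
- Sample size and justification: after stating the power to detect a difference between the groups, the text says "This will be determined using an independent samples t-test".

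**The concern.** No group continues its usual diet. A change from week 0 to week 4 within one group therefore mixes any effect of swapping to lamb with calendar time and with the effect of being observed; for instance, "participants will also be asked to keep a meat diary for the entire duration of the study". The staggered schedule ("Participants will be stagger started as and when they are recruited") spreads calendar effects over participants but does not take them out of a before-after change. Only the randomised contrast isolates the finishing diet.

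The analysis section nevertheless calls the paired result an effect and gives it the same significance level as the randomised test. With a primary objective that can be read group by group, a significant paired test in the grass group could be presented as the answer even if the two groups did not differ. At stake would be a claim for grass-finished lamb that the randomised data do not support.

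**Working it through.** **Inputs.** 16 per group needed and 19 per group recruited; plasma PUFA SD of 2 units; target difference of 2 units; 5% level (all from Sample size and justification). Two-sided tests are assumed. The SD is introduced with the words "Based upon the SD of plasma PUFA of 2 units (%), with 16 in each treatment", which do not say whether it is the SD of change; using it that way below is an assumption.

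**1. The plan's own plasma figure.** Standard error of the difference = 2 × √(2/16) = 0.707. Then 2/0.707 = 2.83, and 2.83 − 1.96 = 0.87, which gives 80.7% power by the normal approximation. The exact t-test gives 78.1% at 16 per group and 85.1% at 19. The stated power reproduces by the normal approximation, and it belongs to the between-group test.

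**2. The bar each test sets.** Let s be the SD of change, equal in both groups.

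- Paired test: observed mean change of t(0.975, n−1) × s/√n
- Between-group test: observed difference of t(0.975, 2n−2) × s × √(2/n)

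| n per group | Paired | Between groups | Paired, s = 2 | Between, s = 2 |
|---|---|---|---|---|
| 16 | 2.131/4 = 0.533 s | 2.042 × 0.354 = 0.722 s | 1.07 units | 1.44 units |
| 19 | 2.101/4.359 = 0.482 s | 2.028 × 0.324 = 0.658 s | 0.96 units | 1.32 units |

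With no observed change in the concentrate group and s = 2 in both groups, an observed grass-group change between 1.07 and 1.44 units (16 per group) would be significant by the paired test and not by the randomised one. The gap arises mainly because one mean has a smaller standard error than a difference of two means. The two tests answer different questions.

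**3. How often the misleading pattern arises.** With no true change in either group, exactly one paired test is significant in 2 × 0.05 × 0.95 = 9.5% of trials. Requiring the between-group test to be non-significant as well lowers this to 6.4%. Only half of these, 3.2%, have the grass group as the significant one, and only half again, 1.6%, show an increase.

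The documents give no expected common change, so a range was assumed. Normal changes with equal SD and the same true mean change in both groups were simulated, 200,000 trials per setting. The table gives the share of trials with the grass group significant, the concentrate group not, and the between-group test not:

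| Common true change (SD of change) | 0 | 0.3 | 0.5 | 0.75 | 1.0 |
|---|---|---|---|---|---|
| 16 per group | 3% | 14% | 23% | 14% | 3% |
| 19 per group | 3% | 16% | 22% | 10% | 1% |

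The between-group test rejected in about 5% of trials in every setting.

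**4. What these figures mean.** When the common change is not zero, a significant paired test correctly detects that the group moved; only crediting the movement to grass finishing would be wrong. The percentages are chances that a pattern appears, and say nothing of how often it would be misreported.

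**5. Would different reporting alter a result?** A 95% confidence interval for the within-group mean change excludes zero exactly when the paired test is significant at 0.05. Replacing the p-values by intervals changes no inference.

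**The case for a change.** The strongest case for a change is that listing a test first is not a rule of inference. The analysis section is short, gives both tests the same level, and calls the uncontrolled one an effect. The primary objective leaves a group-by-group reading open, and one added sentence would cost nothing.

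The facts in this stand. No section calls the paired tests descriptive, the paired test does have the lower bar, and before-after changes here are uncontrolled. What does not stand is the step from there to a fault in the plan. The overall aim, the power statement and the order of the tests all point to the randomised comparison. Nothing says that a within-group result will be used to claim a difference between the meats.

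Demoting the paired tests would also have a cost. The broader purpose in the Background, an effect of eating lamb as such, cannot be addressed by contrasting two lamb groups. The paired tests are the only planned analysis that touches it, however weakly. Barring them from any evidential use would leave that purpose with no analysis.

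**Conclusion.** The concern does not call for a change. Followed as written, the plan gives a sound grass-versus-concentrate comparison with 5% error per outcome, and a valid test of whether each group's mean moved. The gap is an unwritten rule of interpretation, of the kind an analyst fills sensibly: claims about the finishing diet come from the between-group difference, and within-group changes are read as uncontrolled before-after changes.

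The exposure is small without a shared shift, at about 3% of trials per outcome. At 16 per group it peaks at about 23% among the shifts tried. Those figures rest on equal SDs, normal changes and, for the larger values, a common shift that the documents do not give; the thresholds in units rest on taking 2 as the SD of change. Sample size, data collection and the randomised test would be the same with or without a clarifying sentence.
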